Official Title: Linking Biomechanical and Imaging Outcomes to Better Understand the Effects of Running on Knee Joint Health

NCT Number: to be assigned

Document Date: 30-11-2019

Statistical Analysis Plan

All data will be analyzed by our statistician, who will remain independent of all data collection and analyses. Means and standard deviations will be calculated for all outcomes. One factor ANCOVAs will be used to assess between-group differences in running biomechanics outcomes at each biomechanics testing session. At each individual MRI testing session, two factor (group x scan time) repeated measures analyses of covariance (ANCOVAs) will be conducted to examine differences between groups, changes across the MRI scan times (pre-run, immediate-post, 45-minute-post), and any interactions present. Finally, two-factor (group x time) ANCOVAs will be conducted to assess the longer-term effects of the running intervention on biomechanical and MRI outcomes. Treadmill running speed will be a covariate in all statistical analyses, while running mileage during the course of the intervention (defined as % change from baseline) and peak vertical loading rate during the associated biomechanical testing will be additional covariates for MRI outcome changes. To account for the exploratory nature of this research, a significance level of $p = 0.05$ will be used, and no corrections for multiple comparisons will be used. Finally, an exploratory sex-based, sub-group analysis will be conducted to help inform future studies in this area.

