A total of 80 individuals will be recruited for this study: 40 in each group. Groups will be matched for sex, age (+/- 2 years), body mass (+/- 5 kg), and running experience (+/- 1 year). We are unaware of any studies directly relevant to our proposal that would appropriately inform a sample size calculation. Instead, four similar studies have quantified T2 and T1p under loading conditions: Mosher *et al.* 2010, Subburaj *et al.* 2012, and Gatti *et al.* 2017 employed running protocols, but in 37, 20, and 15 young, healthy individuals only; Souza *et al.* 2014 used a lower limb weighting paradigm in a supine position enrolling 44 individuals with knee OA. Thus, our proposed sample of 40 individuals per group is consistent with – and in most cases, exceeds – these studies, and reflects a feasible number within the 5-year timeline proposed for this research.

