After running for 30 minutes, participants will run back to the MRI scanner for an immediate post-run MRI assessment.

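### The SAP gives no rule for a lost scan; a conventional repeated-measures ANCOVA would then drop the runner's other scans from that MRI session, where a mixed model would keep them

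*SAP*

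**What the plan says.** The SAP plans, at each MRI session, that "two factor (group x scan time) repeated measures analyses of covariance (ANCOVAs) will be conducted to examine differences between groups", together with "changes across the MRI scan times (pre-run, immediate-post, 45-minute-post), and any interactions present". That is three scans per session. It adds covariates: "Treadmill running speed will be a covariate in all statistical analyses", and "peak vertical loading rate during the associated biomechanical testing will be additional covariates for MRI outcome changes".

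The SAP does not name an estimation method, a covariance structure or an analysis set. It gives no rule for a missing or unusable scan, or for a missing covariate.

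The Protocol, under Data collection (MRI testing), describes a pre-run scan and then one more: "After running for 30 minutes, participants will run back to the MRI scanner for an immediate post-run MRI assessment". No 45-minute scan appears there. The only related rule concerns the biomechanics day: a run stopped for pain is rescheduled and MRI is postponed. Nothing equivalent is stated for the MRI-day run or for a spoiled scan.

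On size, the Protocol (Participants) says "A total of 80 individuals will be recruited for this study: 40 in each group", and gives precedent and feasibility as the basis because "We are unaware of any studies directly relevant to our proposal that would appropriately inform a sample size calculation". No allowance for losses is stated.

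**The concern.** A least-squares repeated-measures ANCOVA works on one complete row per runner. A runner with good pre-run and immediate-post scans but a lost 45-minute scan drops out of the whole session analysis, including the pre-to-immediate-post comparison that those two scans answer directly. That change is the acute cartilage response the study sets out to measure.

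Two things are at stake. The first is precision, in a sample with no stated reserve. The second is validity, if the runners who lose a scan differ in their cartilage values from those who do not. The TFOA group has knee pain on most days by definition and the controls are pain-free, so loss linked to knee status is plausible. The documents give no evidence on it either way.

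**Working it through.** **Inputs from the documents.** Three scans per session (SAP); two scans per session (Protocol, Data collection); 40 runners per group (Protocol, Participants). The plan's own figure can be checked only as 2 × 40 = 80. No effect size, SD, power or dropout rate is given, so it cannot be reproduced further.

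**Assumptions.** Each scan is lost independently with probability q, taken as 2%, 5% or 10%. Outcome SD is 1 and the correlation between any two scans of a runner is ρ = 0.85. The covariance is treated as known and covariates are left out.

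**Step 1: complete sets.** With k scans the proportion of runners kept is (1 − q)^k.

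| q | three scans | per group | two scans | per group |
|---|---|---|---|---|
| 2% | 0.98³ = 94.1% | 37.6 | 96.0% | 38.4 |
| 5% | 0.95³ = 85.7% | 34.3 | 90.3% | 36.1 |
| 10% | 0.90³ = 72.9% | 29.2 | 81.0% | 32.4 |

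**Step 2: a bound by hand.** Suppose one simply used every runner with both the pre-run and immediate-post scans. That keeps (1 − q)² of runners against (1 − q)³. The SE ratio is √[1/(1 − q)] = √(1/0.95) = 1.026 at 5% and √(1/0.90) = 1.054 at 10%. This part of the loss is due solely to discarding good pairs because the third scan failed.

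**Step 3: complete cases against all available scans.** For the group difference in pre-to-immediate-post change, the complete-case SE is √{2 × 2(1 − ρ)/[40(1 − q)^k]}. At k = 3 and q = 5% this is √(2 × 0.30/34.295) = 0.1323; at q = 10% it is √(2 × 0.30/29.16) = 0.1434. The all-available SE comes from adding the information from each pattern of observed scans, weighted by its probability.

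| scans | q | complete-case SE | all-available SE | ratio | equivalent sample lost, 1 − 1/ratio² |
|---|---|---|---|---|---|
| 3 | 2% | 0.1262 | 0.1243 | 1.016 | 3% |
| 3 | 5% | 0.1323 | 0.1272 | 1.040 | 7.5% |
| 3 | 10% | 0.1434 | 0.1324 | 1.083 | 15% |
| 2 | 5% | 0.1289 | 0.1284 | 1.004 | 0.8% |
| 2 | 10% | 0.1361 | 0.1350 | 1.008 | 1.6% |

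Simulating the random losses in groups of 40 gives 1.041 and 1.086 for three scans, hence 4% and 8–9%. With two scans a runner missing either one has no observed change, so there is almost nothing to recover.

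**Step 4: scale.** At 40 per group and two-sided 5%, the difference detectable with 80% power is (1.960 + 0.842) × √(2/40) = 0.63 SD. With complete three-scan sets only, power for that difference is 73.7% at 5% loss and 66.7% at 10%. This compares complete cases with no loss at all. It is not the gain from changing the method, because a lost scan stays lost.

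**Step 5: bias.** Simulation of 1,500 trials with no true group difference, 40 per group, three scans, correlation 0.7, and the third scan lost in about 5% of controls and 25% of TFOA runners (all assumed). Bias is for TFOA minus control, in SD.

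| loss in TFOA depends on | complete case, average over scans | likelihood on all scans, average | complete case, 45-min minus pre | likelihood, 45-min minus pre |
|---|---|---|---|---|
| nothing | −0.002 | −0.003 | 0.001 | 0.003 |
| the pre-run value | −0.23 | 0.00 | 0.08 | 0.00 |
| the unseen third scan | −0.22 | −0.04 | −0.09 | −0.14 |

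The Monte Carlo standard error of the average bias is under 0.006. Unequal rates alone therefore give no bias. Loss tied to an observed scan biases the complete-case result, and the likelihood fit removes that bias. Loss tied to the unseen scan is only partly corrected, and for the 45-minute contrast the likelihood fit does slightly worse.

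**The case against.** A reader might infer that the SAP restricts the analysis to runners with every scan. It does not say so. Complete cases are the usual behaviour of the named method, and the same factors can be fitted by likelihood. What stands is that the SAP leaves this open, and that the conventional reading of its wording is the one that discards data.

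A reader might also infer that more frequent loss in the TFOA group would by itself bias the group comparison. Step 5 shows otherwise: 5% against 25% loss, unrelated to cartilage values, gave essentially zero bias.

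Even where loss does depend on the pre-run value, the bias falls mainly on mean level. With correlation 0.85 and 25% loss in TFOA, the bias in change from pre-run is only about +0.03 to +0.05 SD, against −0.19 to −0.29 SD in the TFOA mean. This stands, and it makes bias the lesser worry for the acute response.

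The loss rates have no support in the documents, and some safeguards exist. Runners must be comfortable with 30 minutes on a treadmill, they complete such a run about a week before the baseline MRI, and a stopped biomechanics run is rescheduled. These reduce one route of loss but do not cover a scan spoiled by movement or missed on the day.

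Finally, the study calls itself exploratory and says that "a significance level of $p = 0.05$ will be used, and no corrections for multiple comparisons will be used". That lowers the stakes, but it is no reason to discard usable scans when keeping them costs almost nothing.

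**Conclusion.** The point holds in a limited form. The SAP names a method whose conventional form drops a runner's usable scans when one is lost, and it gives no rule to prevent this. With three scans and an assumed 5% or 10% independent loss, the avoidable cost is an SE about 4% or 8–9% larger for the acute change. At 2% loss it is under 2%. These figures assume a correlation of 0.85, and they need the 45-minute scan that only the SAP mentions; with the Protocol's two scans the cost is under 1%. Bias is conditional: it requires loss related to cartilage values or their predictors within a group, which is plausible in symptomatic runners but not documented.

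**What to change.** Specify the within-session analysis as a likelihood-based linear mixed model with group, scan time, their interaction and the planned covariates, an unstructured covariance over scan times, and every usable scan included. Report the contrast of each post-run scan against pre-run, by group and between groups. The unstructured covariance also removes the need to assume sphericity.

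Alongside this:

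- reconcile the SAP's three scan times with the two in the Protocol;
- say how a missing covariate is handled, since the mixed model by itself does not keep a runner without one;
- report scan losses and their reasons by group;
- add a sensitivity analysis for loss that depends on the unseen scan, which the mixed model does not fully correct.

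The cost is SAP wording and slightly more analysis work, with standard software and no new data. The price in assumptions is that the main result then relies on scans being missing at random given what was observed.

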## Study design

This research will comprise two complementary studies to obtain direct and indirect measures of the effects of running on knee cartilage in people with and without TFOA. Biomechanical outcomes will be collected *during* running, while cartilage outcomes will be assessed *before and after* running on a separate day. Comparisons between groups will be made prior to starting a 12-week running intervention (baseline), as well as upon completion (follow-up).

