## Participants

Two distinct groups will be recruited. All eligible participants will be: (i) aged greater than 40 years; (ii) recreational runners who run at least twice per week for a total of at least 10km, and have done so for a minimum of 12 months; and (iii) be comfortable running on a treadmill for 30 minutes. Participants in the TFOA Group will: (i) exhibit radiographic evidence of mild or moderate TFOA according to the Kellgren and Lawrence (KL) OA classification scale (presence of osteophytes and joint space narrowing on X-ray; grades 2 and 3); and (ii) report knee pain on most days of the previous three months (not just during running). Runners in the Control Group will: (i) be free of any radiographic signs of TFOA according to the KL scale (an absence of definitive osteophytes and joint space narrowing; grade 0 – note that we will not be recruiting KL grade 1 individuals due to the potential for early osteoarthritic changes in these individuals); and (ii) be pain-free in both knees for the 12 months prior to recruitment.

Exclusion criteria for both groups will be: (i) any history of traumatic knee injury (defined as one that required surgical intervention or continuous treatment for more than one month); (ii) presence of an inflammatory arthritic condition; (iii) presence of any health condition (other than OA in the TFOA group) affecting normal movement or that precludes engaging in moderate to high impact activities such as running; (iv) use of any oral or injected corticosteroids or viscosupplementation in the previous six months; and (v) any history of surgery in either knee. Furthermore, standard contra-indications to MRI will be assessed for safety purposes.

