#### *Running intervention*

Participants will receive a 12-week running program under the model of building up to a 10 km race. Three weekly training sessions will be planned, and mileage will gradually increase by an average of 10% per week as we have done in our recent running studies. For the purpose of this study, participants will run using their habitual technique – i.e. no specific instructions on ‘how’ to run will be provided at this stage; rather, they will simply be instructed on ‘how much’ to run. A Study Trainer not involved in any aspect of data collection or analysis will oversee the implementation of the intervention via weekly phone conversations with participants to ensure proper adherence and to prescribe appropriate weekly mileage increases. Participants will be provided with a GPS-enabled wrist watch to record their running distance throughout the intervention, which will be supplemented with weekly self-report logs completed online.

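### The longitudinal analysis is described as assessing the effects of the running intervention, but with no non-programme comparator it can only estimate how 12-week change differs by TFOA status

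*SAP*

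**What the plan says.** The SAP states that its two-factor (group x time) ANCOVAs will "assess the longer-term effects of the running intervention on biomechanical and MRI outcomes". Four features of the Protocol determine what those models can estimate.

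- **Who gets the programme.** Under Running intervention: "Participants will receive a 12-week running program under the model of building up to a 10 km race". Neither group is exempted and no arm goes without it.
- **What group means.** Under Participants, groups are defined by disease. TFOA runners have KL grade 2 or 3 and must "report knee pain on most days of the previous three months". Controls must be KL grade 0, that is "be free of any radiographic signs of TFOA according to the KL scale", and pain-free. Group is not assignment to the programme.
- **When people are measured.** Data collection has two time points, baseline and follow-up. There is no untreated run-in.
- **What is compared.** Study design says: "Comparisons between groups will be made prior to starting a 12-week running intervention (baseline), as well as upon completion (follow-up"). That is a between-group aim at each end of the same programme.

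The SAP also enters mileage (percentage change from baseline) as a covariate for changes in MRI outcomes. It is an adjustment term and is not offered as the estimate of the programme's effect.

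**The concern.** An effect of an intervention is a contrast between what happened with it and what would have happened without it. This design observes only the first, in both groups. The SAP sentence therefore claims something that no term in the model delivers.

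What is at stake is how the results are read. The study's title concerns the effects of running on knee joint health. Under the present wording, a significant time effect invites the statement that running changed cartilage for better or worse, and a null group x time result invites the statement that running is safe in TFOA. The design supports neither.

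**Working it through.** **Inputs.** 40 per group, 80 in total (Protocol, Participants). Significance level 0.05 without correction for multiplicity (SAP), taken here as two-sided. The documents give no effect size, SD, power or dropout, so there is no figure of the plan's own to reproduce. Sizes below are assumptions in units of the SD of 12-week change, without covariates.

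**Step 1: what each term estimates.** For each group let P be the programme's effect and S the change that would have occurred anyway (scanner drift, season, retest, natural history).

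- Time effect = ½[(P_TFOA + S_TFOA) + (P_Ctrl + S_Ctrl)]
- Group x time = (P_TFOA − P_Ctrl) + (S_TFOA − S_Ctrl)

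The time effect equals the average programme effect only if S averages zero over the two groups. Group x time equals the difference in programme effects only if S is the same in both groups. It equals the programme effect in TFOA only if, in addition, P_Ctrl = 0. The documents neither state nor support these conditions. Any part of S common to both groups drops out of group x time, and so does any part of P common to both.

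**Step 2: the same by simulation** (40 per group, SD of change 1, 4,000 runs per row).

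| Assumed truth | Time effect: estimate (significant) | Group x time: estimate (significant) |
|---|---|---|
| P = 0; S = 0.3 in both | 0.30 (75%) | 0.00 (5%) |
| P = 0; S = 0.5 in TFOA only | 0.25 (60%) | 0.50 (60%) |
| P = 0.5 in both; S = 0 | 0.50 (99%) | 0.00 (5%) |
| P = 0.5 and S = −0.5 in both | 0.00 (5%) | 0.00 (5%) |

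Row 1: shared drift alone makes the time effect significant and leaves the interaction untouched. Row 2: differential background change produces signals in both terms with an inert programme. Row 3: the interaction misses a real common effect. Row 4: background change hides a real effect from both terms.

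**Step 3: how often drift alone gives a significant time effect.** Noncentral t, 78 df, critical value 1.991, noncentrality = drift × √80:

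- drift 0.1: noncentrality 0.894, probability 0.143
- drift 0.2: noncentrality 1.789, probability 0.424
- drift 0.3: noncentrality 2.683, probability 0.755 (0.75495 before rounding, so 75%)

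**Step 4: what a null interaction would leave open.** The 95% CI for group x time has half-width about 1.991 × √(2/40) = 0.45 SD of change. The difference detectable with 80% power is (1.960 + 0.842) × √(2/40) = 0.63 SD. A non-significant interaction is therefore compatible with sizeable differences between the groups. By Step 1 it also says nothing about an effect that both groups share.

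A larger sample would narrow the interval in Step 4. It would not change the identities in Step 1.

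**The case against.** The strongest reply is that the analysis itself is right. Group x time answers whether change over the programme differs by TFOA status, which is the between-group aim in Study design, and the SAP calls the research exploratory. That stands as a defence of the model. It does not rescue the label: the SAP uses the exploratory nature of the work to justify its significance level, and this does not turn a before-after change into an intervention effect.

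It is also fair that the drift sizes in the working are invented, that the same percentages would hold for any uncontrolled before-after study of 80 people, and that no passage says a null interaction will be reported as safety. The figures are illustrations, and the misreading is a risk that the wording leaves open.

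Several stronger readings are tempting, and the documents do not support them.

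- **That group x time is contaminated by every source of drift.** Sources shared by both groups cancel. Only differential change remains, and matching on sex, age, body mass and running experience narrows some of that.
- **That regression to the mean biases these outcomes because TFOA runners are selected on pain.** The longitudinal analyses are of biomechanical and MRI outcomes, entry also requires radiographic disease, and the pain criterion covers three months. The documents give nothing linking short-term fluctuation in pain to these outcomes.
- **That prior running undermines the contrast.** Both groups are made up of people "who run at least twice per week for a total of at least 10km, and have done so for a minimum of 12 months". This makes the exposure added or structured mileage, not running versus not running. It does not by itself prevent a before-after comparison.
- **That a dose-response on kilometres run would supply the missing evidence.** Mileage is not randomised: it depends on adherence and on the trainer's weekly prescription. Because entry sets only a minimum distance and "mileage will gradually increase by an average of 10% per week as we have done in our recent running studies", absolute kilometres also reflect habitual mileage. Relying on it would bring the causal claim back through a confounded association.

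**Conclusion.** The concern holds as a fault in the stated estimand, not in the choice of model. Neither the time effect nor group x time identifies an effect of the programme. The first is an uncontrolled change over 12 weeks. The second is a difference in 12-week change by TFOA status, free of shared drift but open to differential natural history and blind to a common effect. This follows from three facts in the documents (everyone receives the programme, group is disease status, two time points only) and needs no numerical assumption.

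The size of any resulting error cannot be derived from the documents. Under assumed drifts of 0.1 to 0.3 SD of change, an inert programme would show a significant time effect in 14% to 75% of trials. These figures assume a two-sided 0.05 test, complete data on 80 people and no covariates. The actual drift is unknown and could be close to zero.

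**What to change.** Change the SAP wording as follows.

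1. Define the longitudinal estimand as the difference between TFOA and control runners in 12-week change while following the programme, estimated by group x time and reported with a 95% CI.
2. State that the time main effect is a descriptive change over the programme period and will not be reported as an effect of running.
3. State that a null interaction will not be reported as evidence that running is safe in TFOA.
4. Label any association between outcome change and mileage, including the planned mileage covariate, as exploratory and non-causal.

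No new arm, visit or participant is needed, and the planned models stay. The downside is a weaker claim. To keep the claim of an intervention effect, the study would need a non-programme comparator or an untreated run-in, which is a change of design and not of wording.
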